3.2.2 Usual Care Group

- Adult male and female patients 18 to 75 years old
- HbA1c > 7.5%
- Started on basal insulin in a UPMC Diabetes Outpatient facility within the past three years of study start

• Has blood glucose data available in EMR (At least two HbA1c measurements corresponding to baseline and a subsequent time point after insulin titration) FBG readings)

3.3 Exclusion Criteria

- Pregnant or breastfeeding
- Patients unwilling to use MDC app

4 IRB APPROVAL

The Investigator will obtain, from the University of Pittsburgh Institutional Review Board (IRB), prospective approval of the clinical protocol and corresponding informed consent form(s); modifications to the clinical protocol and corresponding informed consent forms, and advertisements (i.e., directed at potential research subjects) for study recruitment.

The only circumstance in which a deviation from the current IRB-approved clinical protocol/consent form(s) may be initiated in the absence of prospective IRB approval is to eliminate an apparent immediate hazard to the research subject(s). In such circumstances, the Investigator will promptly notify the University of Pittsburgh IRB of the deviation. The Investigator should also notify the sponsor of this event.

The University of Pittsburgh IRB operates in compliance with FDA regulations at 21 CFR Parts 50, 56 and 812, also in conformance with applicable International Conference on Harmonization (ICH) Guidelines on Good Clinical Practice (CGP).

5 RECRUITMENT AND INFORMED CONSENT PROCEDURES

5.1 Recruitment Methods

5.1.1 Intervention Group

Intervention participants will be identified at participating UPMC community-based PC practices, outpatient clinics and inpatient units. A diabetes healthcare provider or staff member (e.g., endocrinologist, PCP, DCES) will identify patients who meet the following inclusion criteria – age, elevated HbA1c, and recommended to start basal insulin – and briefly introduce the patient to the study. The patient may be identified first from a clinic schedule or during the course of their visit. If the patient is interested in learning more about the study, a study investigator (who may also be a diabetes healthcare provider) will provide a more thorough description and a copy of the informed consent for review.

5.1.2 Health Care Group

HCPs (provider participant) who already provide diabetes care and education as part of the patient's routine clinical care will be involved in recruiting individuals for participation in this research study. The PI will formally invite HCPs to join the study, either in person or electronically (via email). A brief overview of the study, the risks and an explanation of their

involvement will be discussed with the potential provider participant. The PI, who is a nurse and DCES, works with and familiar with the HCPs that will be invited to be the provider participants for this study. If an HCP is interested in participating, they will be presented with the consent form.

5.2 Participant Informed Consent Procedures

There are 3 options for obtaining consent:

- 1) Consent process may take place within the diabetes outpatient or primary care setting (Diabetes endocrine satellite clinics or participating primary care sites) or during an inpatient stay.
- 2) Consent process may take place by videoconferencing.
- 3) Consent process may take place by telephone.

Consent will be obtained prior to performing any of the research interventions/interactions.

5.2.1 Consenting in the Outpatient Practice or Inpatient Setting

Potential participants will be presented with the research study and if interested will be presented with the informed consent form. If a potential participant is identified prior to an outpatient clinic visit, they may be presented with the research study by phone and if interested the consent may be sent to them by mail or email for them to review prior to their clinic visit.

Potential participants are ensured that their decision to participate is totally voluntary and in no way will jeopardize their diabetes care or education services. Patients will be given sufficient time to come back to the study team regarding any questions that they may have and their decision. After reading/explaining the consent and study procedures, the study team member will ask the participant if they have any questions (general) and then re-review the study procedures one more time to ensure that they are fully understood.

5.2.2 Process for Videoconferencing Consenting

- Study staff sends two copies (one to send back and one to keep) of the consent (via email or USPS) to the potential participant and schedules a video diabetes education visit to occur about a week later. In addition to the consent forms, they will also be provided a self-addressed, stamped envelope.
- During the video visit, the participant must have a hard copy in front of them as the study staff reads it, and if they agree, will sign in front of the study staff by video.
- The participant will hold up their signed signature page and study staff will take a "screen shot" print it out to be attached to the study staff signed consent form. Another option is for the patient to take a picture of their signed signature page and upload into their MyUPMC account for the study staff to access.
- The participant will be instructed to mail their original signed copy of the consent form to study staff using the self-addressed, stamped envelope.

 Research procedures can start via video visit after the study staff gets the screen shot of the participants signature page.

Potential participants are ensured their decision to participate is totally voluntary and in no way will jeopardize their diabetes care or education services. Patients will be given sufficient time to come back to the study team regarding any questions that they may have and their decision. After reading/explaining the consent and study procedures, the study team member will ask the participant if they have any questions (general) and then re-review the study procedures one more time to ensure that they are fully understood.

6 POTENTIAL RISKS AND BENEFITS

6.1 Potential Risks

The potential risks associated with participation in the study are of low frequency and of low/acceptable risk level.

There is little likelihood of physical risk because of participation in this study. Patients will not undergo any clinical procedures beyond those used during usual diabetes care. Collection of clinical data will follow usual care procedures and be performed by trained clinical staff. As is usual, patients may experience some physical discomfort during clinical procedures.

MDC is prescribed by the HCP with a therapy plan. A detailed risk analysis (user and product) has been conducted to evaluate all possible risks to the end user. An example of such a risk is how likely an overdose, attributed to an incorrect dose recommendation, will lead to serious hypoglycemia.

All such risks have been mitigated in the design of all the products and/or via risk control measures to prove that the produce is safe for use.

Within the context of this study, a favorable benefit-risk balance for the provided Sanofi medicinal products (Toujeo and Lantus) is already well established. The use of both drugs in this study is according to the approved National Product Label.

Patients are at low risk for psychological harm as no research procedures are performed in addition to usual care except for the addition of technological support and the administration of questionnaires. The only potential risk is that patients may not fully understand the technology process or experience frustration. Clinical personnel will be asked questions that have low psychological risk and may refuse to provide answers to any questions they are not comfortable answering or if in any way they feel that answering questions may jeopardize their employment or practice communications. Clinical personnel also run the potential risk of frustration with the technology process or perceive additional burden or experience disappointment with any unintended technological challenges in the process.

There is little social risk associated with this study. Patients are at low risk to social harm as no research procedures are performed in addition to usual care except for the addition of the

technology. For clinical personnel, questions will not go beyond the topic of healthcare delivery. HCP participants may perceive that feedback may be used to rate their performance; however, this is not the case and all responses will be kept anonymous. HCP participants may find the additional of technology to pose a potential disruption in office workflow.

There is a small possibility of a breach of confidentiality. Procedures will be put in place to minimize this risk. All participant questionnaires will be de-identified and kept in a double locked environment (paper questionnaires) or a secure server (electronic questionnaires).

6.2 Alternative Treatments

Patients who decline participation in this study will receive usual care for insulin dosing.

6.3 **Potential Benefits**

This study may contribute to the participants' ability to better self-manage their diabetes and provide valuable information on a process that has the potential to add evidence for broad best practice guidelines and policy. We are enthusiastic about the opportunity to implement a model MDC app that helps patients perform titration effectively to achieve their target goal and maintain improvement as compared to the current manual practice.

7 RISKS MANAGEMENT PROCEDURES

The nature of this study places patients at low risk to physical, psychological or social harm. Patients will not undergo any procedures beyond usual care except for the addition of access to clinical, health, and self-management support delivered through technology. Patients and clinical personnel who participate will be free to refuse to respond to any survey questions. All responses will be kept anonymous and not linked to any identifying information.

Only the minimum amount of data necessary for answering the proposed research questions will be extracted from the medical records. Patients will be assigned unique, study-specific identifiers. No clinical data will be linked to medical record numbers. A file linking patients to subject identifiers will be stored separately and securely from de-identified patient clinical data. Clinician participant data will be collected anonymously. Any identifying information will be eliminated from surveys. All research data will be stored on encrypted and password protected network drives. Access to patient-level data will be limited to members of the research team involved in data collection. All other members of the research team will review de-identified data.

All research interventions/activities will be conducted in private. The collection of sensitive information about subjects is limited to the amount necessary to achieve the aims of the research, so that no unneeded sensitive information is being collected.

Any paper records with patient identifying information will be store behind a double locked environment. An electronic password-guarded study database may be used under the supervision of the Investigator for this protocol with data being entered anonymously with a subject code behind a UPMC and/or University of Pittsburgh's secure computer server. Information linking subject identifiers with the coded subject number will be stored under password protection on computers in locked areas, with access only to the database manager.

All staff will sign confidentiality statements. Access to the database will be limited to the data manager and staff under the supervision of the Investigator.

All staff involved in this study are properly credentialed and instructed in the areas of testing, confidentiality, and safety.

The PI will retain the data for the entire period of this study and will retain the specified records and reports for up to seven years at least seven years after final reporting or publication of the study. If the subject and/or legal representative decide to withdraw or be withdrawn from study participation, they may request that the study data and samples be destroyed. Subject names or other directly identifiable information will not appear on any reports, publications, or other disclosures of clinical study outcomes.

8 **REPORTABLE EVENTS**

Each patient will be carefully monitored for adverse events by the investigator.

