2.2.3 Intervention Group

Phase 1 (Titration)

Baseline Visit

Patients assigned to the intervention group will meet with a DCES and receive insulin therapy education according to current standard of care procedures (e.g., how to use an insulin pen, when and where to administer insulin, etc.). Whereas DCESs typically provide patients with written titration instructions prepared by the physician provider, for the intervention, DCESs, another HCP and/or a trained clinical research coordinator will train patients to use MDC-T for titration guidance. The physician provider will prepare an individualized titration algorithm, including a dose plan and dose adjustment rules that will be embedded in MDC-T. The DCES, another HCP, and/or clinical research coordinator will demonstrate to the patient how to use the MDC Titration Module to determine and guide dosing adjustments.

All patients will be asked to complete a baseline survey to assess behavioral and psycho-social factors that may influence diabetes self-management. In addition, patients will receive a threemonth supply of insulin pens (Lantus (U100) Solostar Pen or Toujeo (U300) Solostar Pen, as per treating Physician).

Patients will be instructed to return for a three-month follow-up clinic visit, as is standard of care for patients new to insulin.

Month 3 Visit

At the three-month appointment, the DCES or another HCP will assess the patient's experiences with titration and MDC-T, which will be documented using a study-specific survey. If the patient successfully reached their glycemic target, they will be invited to participate in Phase 2 of the study (maintenance).

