For those patients who do not reach target at 3 months, the DCES/HCP will partner with the patient (and physician provider, as needed) to assess the patient's ability and interest in continued use of the MDC-T app and determine the best course of action (either return to usual care or continued participation in the study). If deemed eligible, the patient will continue to have access to the MDC-T app with continued guidance from their respective HCP, in regards to insulin therapy recommendations. They will be asked to complete follow-up surveys at months 3 and 6, as well as permit access to pertinent medical record information (e.g., HbA1c values) for the duration of the study. Patients who stay in the study and continue to use the MDC-T app will receive another three-month supply of insulin pens (Lantus (U100) Solostar Pen or Toujeo (U300) Solostar Pen, as per treating Physician).

Phase 2 (Maintenance)

Patients who are successful in reaching their glycemic target and agree to continue participation, will be transitioned into Phase 2 of the study at their three-month clinic visit. At this time, the HCP (endocrinology provider and/or DCES) will introduce and train patients how to use the MDC-M app to support glycemic control. Patients will receive another three-month supply of insulin pens (Lantus (U100) Solostar Pen or Toujeo (U300) Solostar Pen (as per treating Physician) and asked to return for the final follow-up visit at six months (routine clinic visit). They also will be asked to complete follow-up surveys at months 3 and 6 to assess changes in behavioral and psychosocial factors that influence diabetes self-management as well as their acceptability and satisfaction with their experience using the MDC app. When possible, surveys will be completed at clinic visits. However, surveys may also be made available electronically or via mail should visits occur remotely (e.g., via telemedicine) or a patient cannot complete at a face-to-face visit (e.g., time constraints).

The DCES and endocrinology provider will be available throughout the course of the study to respond to any question or concerns that the patient may have regarding insulin titration, insulin dosing, and the MDC app specifically.

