2.5.2 Secondary Endpoints

2.5.2.1 Phase 1 (Titration)

- Change in HbA1c from baseline to 3 months within and between groups
- Proportion of patients reaching HbA1c <7% at 3 months as compared to patients using SOC
- Change in FPG from baseline to 3 months within and between groups
- Patient-reported changes in behavioral and psychosocial outcomes from baseline to 3 months (survey)
- Patient-reported acceptability of and satisfaction with MDC-T (survey)
- Provider-reported acceptability of and satisfaction with MDC-T (survey)
- Rate of escalation to Endo (Endocrine visits) for patients using MDC-T
- Safety end points (including hypoglycemia, any untoward adverse events)
- Number and type of technical complaints

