11.2 Payments

Patients will receive \$20 for completing the baseline survey and \$50 for each completed survey at 3 and 6 months. In addition, \$100 per participant will be allotted for HCPs as remuneration for their time spent on study-related activities (e.g., consenting participants, survey administration, instructing patients on MDC, etc.).

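### Patient surveys are called anonymous and unlinked although the change endpoints need them coded by study ID, and nothing keeps the answers from the staff who train patients on the app

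*Combined protocol and SAP*

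**What the plan says.** **Status of survey answers.** Section 7, after noting that patients and clinical staff may decline any survey question, states: "All responses will be kept anonymous and not linked to any identifying information". The same section says "Patients will be assigned unique, study-specific identifiers" and "A file linking patients to subject identifiers will be stored separately and securely from de-identified patient clinical data". It describes an optional study database "with data being entered anonymously with a subject code", with the key held separately. Section 6.1 calls participant questionnaires de-identified.

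**What the surveys must deliver.** Section 2.5.2.1 lists "Patient-reported changes in behavioral and psychosocial outcomes from baseline to 3 months (survey") as a secondary endpoint. Section 2.5.2.2 lists the corresponding change from baseline or month 3 to later time points. Both sections are fed by the DMSRQ-SF and DDS17, which the study calendar schedules at every visit. Section 2.6.2 plans descriptive statistics for surveys, in the intervention group only.

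**Who collects them.** Section 2.2.2 gives health care professionals (HCPs) the tasks of recruiting, training and supporting patients and obtaining study data. At month 3, under Section 2.2.3, "the DCES or another HCP will assess the patient's experiences with titration and MDC-T", recorded on a study-specific survey. Section 11.2 allots HCPs 100 dollars per participant for time on tasks that include "survey administration, instructing patients on MDC". Completion at the clinic is preferred, but under Section 2.2.3 "surveys may also be made available electronically or via mail" if the visit is remote or the patient cannot complete the survey there.

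**The concern.** There are two separate problems, and both affect the patient surveys.

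The first is linkage. A change endpoint is built from one person's answers at two visits. A site that takes the Section 7 sentence at face value could reasonably leave the study ID off the form. Once forms have been collected without a code, the link cannot be restored. The precision of the change estimates would suffer, and so would the ability to compare like with like once the cohort narrows to those who reached target.

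The second is who asks. Patients may be questioned about an app by the care team that introduced it and taught them to use it. The study is open label, and app acceptability has no comparator. If patients soften criticism out of courtesy, nothing in the design would reveal or offset it. Patient acceptability is part of the secondary objective in Section 1.1.2.

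**Working it through.** **1. The plan's own figures.** Section 2.6.1 gives 109 per arm, an SD of 1.5 for HbA1c change and a precision of ±0.40. With a 95% interval, 1.96 × 1.5 × sqrt(2/109) = 0.398, so the figure reproduces. Phase 2 entry is 0.70 × 109 = 76.3, stated as 76. The plan gives no figure for the surveys, and the HbA1c precision does not depend on them.

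**2. Can linkage be read into Section 7?** The restrictive sentence bars a link to identifying information. It does not expressly bar a study code, and elsewhere the section uses the word anonymously for data entered under a subject code. However, the linking file is described in relation to clinical data, the coded database is only optional, and no sentence puts the study ID on a survey form. Linkage is therefore permitted on one reading and secured on none.

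**3. Cost if the sentence is followed literally.** Let σ be the survey SD (taken as equal at both visits), n the number completing both surveys, and r the within-patient correlation. The documents do not give r, so it is assumed.

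- Linked: SE of mean change = σ × sqrt(2(1−r)/n)
- Unlinked: SE that can be reported = σ × sqrt(2/n), because r cannot be estimated
- Ratio = 1/sqrt(1−r)

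The 95% half-widths below are 1.96 × SE, in units of σ. They assume complete surveys in all 109 or all 76 patients.

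| r (assumed) | Ratio | n = 109 linked | n = 109 unlinked | n = 76 linked | n = 76 unlinked |
|---|---|---|---|---|---|
| 0.3 | 1.20 | 0.222 | 0.265 | 0.266 | 0.318 |
| 0.5 | 1.41 | 0.188 | 0.265 | 0.225 | 0.318 |
| 0.7 | 1.83 | 0.145 | 0.265 | 0.174 | 0.318 |
| 0.8 | 2.24 | 0.119 | 0.265 | 0.142 | 0.318 |

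If the same patients answer both times, the difference in means is the same either way. What is lost is the individual change scores, their SD and the narrower interval.

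**4. Selection into Phase 2.** The 76 entrants are those who reached target and agreed to go on, which leaves 109 − 76 = 33 others. Without a code, the only available baseline is that of all 109. If entrants and others differ at baseline by d, the mean of all 109 differs from the entrants' own mean by (33/109) × d = 0.30 × d. That amount would appear as change although nobody changed. The documents give no value for d.

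**5. Separation of carer and collector.** Section 2.2.3 allows app training by a diabetes care and education specialist (DCES), another HCP or a research coordinator. It allows the month 3 assessment by a DCES or another HCP. The roles overlap, and the same individual is neither required nor excluded. Section 2.4.3 specifies a patient version of the acceptability and satisfaction survey, and Section 2.2.3 says patients complete the surveys. Section 11.2, however, counts administering surveys among the paid HCP tasks. Section 7 promises that research activities take place in private, which concerns the setting. It does not say that the treating team will not see the answers.

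**The case against.** The strongest reply on linkage is that Section 7, read as a whole, describes coded data: identifiers, a subject code and a separate key. A reader might infer from the disputed sentence that change cannot be computed at all. The documents do not support that, since removing identifying information is compatible with keeping a code, and even unlinked surveys would give a difference in means. Nor do the payments to patients for each completed survey prove that answers are linked; they need only a record of completion. The analysis is also descriptive, with no paired test named. All of this stands. What remains is that the change endpoints rely on a code that no text places on the form.

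On collection, a reader might infer that satisfaction is inflated, or that HCPs are paid to obtain favourable answers. Neither follows. The payment is for time and does not depend on the responses. The assessor need not be the trainer. The endpoints are patient-reported, and nothing suggests that the DMSRQ-SF or DDS17 is scored by staff. The month 3 sentence may describe an ordinary clinical conversation. The secondary objective also covers workflow and HCP acceptability, and the HCP portion is a separate submission. Patient use is tracked through device analytics as well. These points limit the concern to a plausible risk, but they do not remove it: staff administration is foreseen, and nothing shields the answers from the care team.

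**Conclusion.** The concern holds in a limited form, for secondary and descriptive outcomes only.

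The Section 7 sentence conflicts with the survey change endpoints and with the coded and de-identified wording elsewhere. If applied literally, it would widen intervals for mean change by a factor of 1.20 to 1.83 for assumed r of 0.3 to 0.7, and by 2.24 at r = 0.8. It would also prevent the Phase 2 entrants from being compared with their own baseline. If sites code the forms anyway, neither loss occurs, so this part is close to a wording correction.

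Patient-reported acceptability and satisfaction are at risk of upward bias because the roles that train and support patients may also collect the answers. The likely direction favours the app, but the documents give no basis for a size. The HbA1c endpoints are not touched. Both points are worth correcting before surveys are collected, because neither can be repaired afterwards.

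**What to change.** 1. In Section 7, replace the anonymity statement, as it applies to patient surveys, with: *confidential, coded by study ID at every time point, and not visible to the treating HCP*. Use the same term in Section 6.1 and in the consent form. The identifier system already exists.
2. Have the acceptability and satisfaction survey, and preferably the DMSRQ-SF and DDS17, self-completed in private. Patients can do this on paper at the visit or through the electronic or mail routes already in Section 2.2.3. Staff may hand over the form but should neither ask the questions nor see the answers.
3. Reword the month 3 text in Section 2.2.3 so that the HCP's conversation about the patient's experience is separate from the patient-completed survey that supplies the endpoint.

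The cost is protocol and consent wording, plus a possible small loss of response when staff no longer administer the form. The existing payment of 50 dollars for each completed survey at months 3 and 6 should limit that loss.
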